### **Analysis Plan and Power Calculations:**

We will test the hypothesis that RMs/UMs (1 or 2 gain-of-function alleles) in the genotype-supported arm have better GERD and symptom control than RMs/UMs in the conventional treatment group because they will have their dose increased based on their genotype.

Continuous variables will be compared between the genotype-supported group and the conventional treatment group using the Student's unpaired *t*-test, and categorical variables will be compared using the chi-square or Fisher's exact test. The hypotheses will be tested using linear regression analysis to estimate the difference in the RDQ reduction in the RM/UM patients between the two arms. All analysis will be performed in SAS 9.4 (Cary, NC).

We will evaluate the percentage of the time when a dosing recommendation was made and accepted by the treating clinician, to provide practical data on the willingness of clinicians to adopt this approach. We will also collect patient- and provider-level survey data on knowledge, attitudes, and beliefs about pharmacogenetics testing, using survey tools adapted from other IRB-approved studies.

Power calculation. While there are no data in the literature on genotype associations with the efficacy endpoint we will use (symptom improvement), there are pH probe data by genotype that were generated by the Nemours investigators, that we can use, and this should be an excellent surrogate for symptom data. We have done power calculations based on two of the pH-based response phenotypes, found in Table 3. Specifically we powered based on percent time with pH < 4 (which has an effect size of 0.79) and acid clearance time (effect size of

0.45). Based on these two phenotypes, we have the following power to detect differences in efficacy between *CYP2C19\*17* carriers and non-carriers:

Based on the previous data for acid clearance time, with 180 total participants (120 from UF Health and 60 from Nemours), we have 81% power to detect a 0.49 effect size.

Based on the previous data for time with pH <4.0, with 180 participants, we have >99% power to detect a 0.79 effect size.

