With 180 total patients (90 patients in each arm), we expect approximately 30 patients in each arm to have the genotype of interest (i.e. RM or UM). At alpha of 0.05, we will have 80% power to detect effect size of  $\geq 0.74$  in the RDQ score in RMs/UMs. This effect size is equivalent to a RDQ score difference of 1.22 for regurgitation and a score difference of 0.93 for heart burn. These differences in RDQ scores are smaller than what is considered clinically significant. Therefore our study is well-powered.

In summary, by studying a total 180 patients (120 from UF Health and 60 from Nemours), the data suggest we will have excellent power to detect an efficacy endpoint. Data generated from this protocol on adverse effects will also help us define the incidence of the adverse effect phenotypes to inform sample size for a future pragmatic trial examining effects of genotype-supported dosing on PPI safety endpoints.

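### The acid-clearance power figure pairs 81% with an effect size of 0.49 where the plan's own effect size is 0.45, and both pH-based power figures are for genotype carriers versus non-carriers, not for the planned between-arm RM/UM test

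*Combined protocol and SAP*

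**What the plan says.** All of this is in section 7 (Research Plan) of the UF protocol, under Analysis Plan and Power Calculations, unless noted.

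- **Planned test.** Linear regression is to "estimate the difference in the RDQ reduction in the RM/UM patients between the two arms".
- **Basis of the pH figures.** The plan uses pH-probe data from Table 3 as a surrogate for symptoms: "Specifically we powered based on percent time with pH" below 4 (effect size 0.79) and "acid clearance time (effect size of" 0.45).
- **Contrast for those figures.** They are introduced with "we have the following power to detect differences in efficacy between" CYP2C19\*17 carriers and non-carriers.
- **Power lines.** For acid clearance with 180 participants, "we have 81% power to detect a 0.49 effect size". For time with pH below 4, "we have >99% power to detect a 0.79 effect size".
- **Separate calculation for the planned test.** With 90 patients per arm, "we expect approximately 30 patients in each arm to have the genotype of interest" (RM or UM). The plan continues: "At alpha of 0.05, we will have 80% power to detect effect size of" 0.74 or more in the RDQ score.
- **Summary.** The section ends by calling the power for an efficacy endpoint excellent. The opening of section 7 also refers forward to the power calculation to support the total of 180.

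**The concern.** Two different effect sizes are printed for one measure, a few lines apart, and only one of them can go with 81%. A reader who takes the power line at face value gets a wrong pairing. A reader who goes back to Table 3 for the right value does not find either number there.

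The second issue is what the figures are about. The 81% and >99% compare people who inherited a \*17 allele with people who did not, across both arms. Randomisation does not protect that comparison, and this analysis section describes no analysis that makes it. The trial's hypothesis compares the two arms within RM/UM patients, which is about one third of the sample. Because the pH figures are described as what the study was powered on, and sit shortly before a favourable summary, they can be taken as support for the randomised comparison. They are not.

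**Working it through.** **Inputs**
- Total 180, 90 per arm, about 30 RM/UM per arm: Power calculation. This gives 60 carriers and 120 non-carriers.
- RM/UM share: 28% + 5.3% = 33.3% (Table 1); about 30% to 35% (Genotyping and result reporting), or 54 to 63 of 180.
- \*2/\*17: 5.6%, phenotype marked as unknown (Table 1).
- Acid clearance, mean (SD): 181 (271), n = 21, and 107 (158), n = 53 (Table 3).
- Alpha 0.05 is stated for the RM/UM calculation. I assume that it also applies to the pH figures, that tests are two-sided, and that there is no attrition, since no allowance is stated.

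**Formula.** Two-sample t-test with noncentrality d × √(n1·n2/(n1 + n2)), and power from the noncentral t distribution.

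**Step 1. The printed acid-clearance figure, 60 v 120.** √(60 × 120/180) = √40 = 6.325.
- d = 0.49: 0.49 × 6.325 = 3.099, power 86.9%.
- d = 0.45: 0.45 × 6.325 = 2.846, power 80.8%.

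The stated 81% does not reproduce at 0.49. It does at 0.45.

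**Step 2. Other carrier counts**

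| Split | Source | Power at 0.45 | Power at 0.49 |
|---|---|---|---|
| 54 v 126 | 30% share | 78.6% | 85.0% |
| 63 v 117 | 35% share | 81.7% | 87.7% |
| 70 v 110 | \*2/\*17 counted as carriers (38.9%) | 83.3% | 89.0% |
| 60 v 109 | \*2/\*17 left out (39% + 20% + 1.7% = 60.7% non-carriers) | 79.5% | 85.8% |
| 51 v 129 | Table 3 share, 21/74 | 77.2% | 83.8% |

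At 0.49 the power runs from 83.8% to 89.0%. To get 81% at 0.49 would take about 45 carriers of 180 (25%), below the plan's own share.

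**Step 3. Table 3.** The difference is 181 − 107 = 74. The pooled SD is √[(20 × 271² + 52 × 158²)/72] = 196.
- 74/196 = 0.38, with power about 67% at 60 v 120.
- 74/158 = 0.47 (comparison-group SD), with power about 84% at 60 v 120.

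Neither calculation returns 0.45 or 0.49. The 0.79 cannot be checked this way, because Table 3 gives no SD for percent time with pH below 4.

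**Step 4. The pH < 4 line.** At 60 v 120, d = 0.79 gives 99.9%, so >99% reproduces for carriers versus non-carriers.

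**Step 5. The planned test, 30 v 30.** √(30 × 30/60) = 3.873, and 0.74 × 3.873 = 2.866, power 80.5%. The plan's 80% reproduces; the exact effect for 80% is 0.736.

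**Step 6. Who supplies the RDQ.** The UF protocol (Assessment of PPI efficacy and adverse effects) names the RDQ. The Nemours protocol (Assessment of PPI adverse events and efficacy) lists the GASP-Q, the PedsQL Gastrointestinal Symptoms Module and the SN-5, and not the RDQ. If only the 120 UF adults contribute, 120 × 1/3 = 40 RM/UM patients, or about 20 per arm. Then √(20 × 20/40) = 3.162, 0.74 × 3.162 = 2.340, power 62.6%. At that size 80% power needs an effect of about 0.91.

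**The case against.** The strongest reply is that 0.49 is probably a typing error for 0.45: the 81% is right for 0.45, and the slip understates power. That is fair, and nothing about enrolment follows from it. The printed pair still needs correcting, and restoring 0.45 alone would leave a value that Table 3 does not yield directly.

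It can also be said that 81% at 0.49 is wrong only under assumptions. With 15% attrition (51 v 102), 0.49 does give 81.0%. But the plan states no attrition allowance and ties the line to 180 participants. It would also leave the two effect sizes in conflict.

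On the contrast, the plan labels the figures openly as carriers versus non-carriers, and it powers the planned test separately. The forward reference at the start of section 7 can be read as covering the whole power section. The favourable summary follows an argument that the detectable RDQ differences (1.22 for regurgitation, 0.93 for heartburn) are below what is clinically significant, so it need not rest on the pH figures. The Nemours document also foresees secondary analyses by genotype-inferred phenotype, although it does not tie them to the RDQ. All of this stands, and it limits the point to labelling and to what the summary may rest on.

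A reader might go further and infer that the randomised comparison has no power calculation, or that its power is only 40% (at 0.45) to 46% (at 0.49) with 30 per arm. The documents support neither. The RM/UM calculation is there and reproduces. The lower figures would require the pH effects between genotype groups to apply between arms, which the plan does not say.

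**Conclusion.** The point holds, as a reporting correction and not as a finding that the trial is undersized. The acid-clearance line is wrong as printed: about 87% goes with 0.49 and about 81% with 0.45, at 60 v 120, two-sided 0.05 and full retention. The conclusion survives every carrier split that the documents support. Which effect size was meant cannot be settled from the documents, since Table 3 gives 0.38 or 0.47 depending on the SD.

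The 81% and >99% figures say nothing about the power of the randomised comparison. The only figure that does is 80% at 0.74 or more. Its arithmetic is right, but it needs about 30 RM/UM patients per arm with RDQ data, and so all 180 patients. The documents do not settle whether the Nemours children supply the RDQ; the Nemours protocol does not list it. If they do not, the figure is about 63% at 0.74, or 80% at about 0.91. That is conditional, and should be stated as such.

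**What to change.** 1. Re-derive the acid-clearance effect from Table 3, state which SD was used, and print the power that goes with it, together with the carrier count and the handling of \*2/\*17.
2. Label the two carrier-contrast figures as genotype-association figures that do not power the randomised comparison.
3. Rest the summary power statement on the RM/UM between-arm calculation alone, and say that 80% at about 0.74 assumes RDQ data from all 180 patients. If only the 120 UF adults supply the RDQ, state instead about 63% power at 0.74, or 80% power at about 0.91, with about 20 RM/UM patients per arm.

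The cost is wording only: no change to enrolment, test or data collection. The stated power becomes less favourable.

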Collectively, these preliminary data provide compelling evidence for the potential clinical utility of *CYP2C19*-genotype supported dosing by documenting 1) the relationship between *CYP2C19* genotype and PPI pharmacokinetics, 2) that response to PPI therapy, based on gastric pH, is influenced by *CYP2C19* genotype, and 3) that patients are undergoing risky, invasive procedures who may simply need a higher dose of PPI to overcome their RM phenotype status.

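### The 81% and >99% power figures apply an effect seen without genotype-based dosing to a pool in which about half the carriers are assigned to a recommended dose increase

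*Combined protocol and SAP*

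**What the plan says.** Section 7 of the UF Health protocol, under Analysis Plan and Power Calculations, sets out the hypothesis that rapid and ultra-rapid metabolizers (RM/UM) in the genotype-supported arm do better than RM/UM patients in the conventional arm, "because they will have their dose increased based on their genotype". The test is a linear regression of RDQ reduction among RM/UM patients, arm against arm.

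The power paragraph then turns to pH-probe data: "Specifically we powered based on percent time with pH < 4 (which has an effect size of 0.79) and acid clearance time (effect size of". The acid-clearance value that completes this sentence is 0.45. The results are introduced with "we have the following power to detect differences in efficacy between", and the two groups named are patients with and without a \*17 allele. For acid clearance the basis is "with 180 total participants (120 from UF Health and 60 from Nemours"), and the claim made on it is that "we have 81% power to detect a 0.49 effect size". For time with pH below 4, "with 180 participants, we have >99% power to detect a 0.79 effect size".

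A further calculation in the same section addresses the planned contrast: "we expect approximately 30 patients in each arm to have the genotype of interest (i.e. RM or UM"), with 80% power at an effect size of 0.74. The closing summary describes the power for efficacy as excellent.

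Under Genotyping and result reporting, the same section says that a dose-increase recommendation goes out for RMs and UMs and that the final prescribing decision stays with the physician. Section 5 closes by describing patients "who may simply need a higher dose of PPI to overcome their RM phenotype status".

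**The concern.** The two pH-probe effect sizes come from Table 3: 74 children on PPI therapy, 21 \*17 carriers and 53 others, with no genotype-based dosing described. They measure how much worse carriers do when dosing takes no account of genotype. The protocol attaches them to all 180 participants, but about half of the trial's carriers are assigned to an arm whose purpose is to reduce that deficit. No section restricts the carrier comparison to the conventional arm or lowers the effect size for carriers in the genotype-supported arm.

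At stake is how a reader judges the power of the trial. Two of the three efficacy power statements, and the summary that follows them, describe a difference that gets smaller as the intervention succeeds.

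**Working it through.** **Inputs**
- Carriers: about 30 RM/UM in each arm of 90 (section 7), so 60 carriers and 180 − 60 = 120 non-carriers.
- Effect sizes d: 0.79 for time with pH below 4; 0.45 where acid clearance is introduced and 0.49 in its power sentence.
- Alpha 0.05. Sidedness is not stated, so two-sided is assumed. SD is 1 in every group. No dropout is stated and none is applied.

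**Formula.** Two-sample t-test with noncentrality d / √(1/n₁ + 1/n₂) and n₁ + n₂ − 2 degrees of freedom.

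**Step 1: reproduce the printed figures.** For 60 v 120, √(1/60 + 1/120) = 0.158.
- d = 0.79: noncentrality 5.00, power 99.9%. This matches >99%.
- d = 0.45: noncentrality 2.85, power 80.8%. This matches 81%.
- d = 0.49: noncentrality 3.10, power 86.9%. This does not match 81%. A split of about 45 v 135 would give 81% at 0.49, but no section supports 25% carriers.

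**Step 2: conventional arm only.** For 30 v 60, √(1/30 + 1/60) = 0.224. Power is 93.8% at 0.79, 51.2% at 0.45 and 58.2% at 0.49. None of these matches the printed figures. The printed figures therefore count the carriers of both arms, each at the full deficit.

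**Step 3: allow for the intervention.** Let k be the share of the carrier deficit removed, on average, among carriers in the genotype-supported arm. Incomplete uptake lowers k. Half the carriers keep a deficit d and half have (1 − k)d, so the pooled effect is d(1 − k/2).

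| Comparison | d = 0.45 | d = 0.49 | d = 0.79 |
|---|---|---|---|
| All 180, k = 0 (as printed) | 80.8% | 86.9% | 99.9% |
| All 180, k = 0.5 | 56.5% | 63.7% | 96.1% |
| All 180, k = 0.75 | 42.4% | 48.7% | 87.4% |
| All 180, k = 1 | 29.3% | 33.8% | 70.0% |
| Conventional arm only, 30 v 60 | 51.2% | 58.2% | 93.8% |

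At k = 1, for example, the pooled effects are 0.79 × 0.5 = 0.395 and 0.45 × 0.5 = 0.225. A simulation gives 68% in place of 70.0% at d = 0.79 and k = 1, and otherwise agrees within about one percentage point. Counting \*2/\*17 patients as carriers (5.6% of 180, about 10 more, so 70 v 110) gives 73% and 31% at k = 1 for 0.79 and 0.45.

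**Step 4: how soon each figure fails.** At 0.79, power stays at or above 99% until k is about 0.27, and above 90% until k is about 0.70. At 0.45, power is down to 79% at k of about 0.05.

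**Step 5: the planned contrast.** RM/UM patients, 30 v 30: √(2/30) = 0.258, so d = 0.74 gives noncentrality 2.87 and power 80.5%. The printed 80% reproduces. It uses neither pH-probe effect size.

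**The case against.** The strongest reply is that each printed sentence is conditional. It gives power to detect a stated effect size, and given 0.79 or 0.45 the arithmetic is right. That stands: this is not a calculation error. But the protocol introduces both figures as based on the previous data and uses them as efficacy power for this trial, which takes the pediatric effect to be present in full across the pooled sample.

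A second reply is that the dilution may be modest. The genotype-supported arm receives a recommendation, which the physician may decline, and acceptance is itself something the study measures. The Abstract (section 3) notes that some RM/UM patients do not respond even to an increased dose, and section 5 says only that patients may need a higher dose. This also stands. Full removal (k = 1) is an extreme, and the lower values of k deserve as much attention.

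A third reply is that the planned contrast has its own calculation, which is correct. This stands too and limits the consequence: neither sample size nor analysis depends on the two figures.

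A reader might infer more than the documents support. One inference is that the figures hold only if the trial's hypothesis is false. The hypothesis asks for better control, not for the deficit to vanish, and >99% survives removal of roughly a quarter of it. Another is that the planned analysis is biased towards no genotype effect. The UF Health analysis plan contains no carrier v non-carrier efficacy test over all 180, so that bias would arise only if someone added one.

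**Conclusion.** The point holds as a misapplied assumption. The 81% and >99% are correct for about 60 v 120 at 0.45 and 0.79, but they apply an effect observed without genotype-based dosing to a pool in which about half the carriers are assigned to a recommended dose increase. The 81% has almost no margin. The >99% tolerates a partial benefit, and power at 0.79 remains high (about 96%) with half the deficit removed.

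The result rests on a two-sided test, equal SDs, no attrition, the protocol's own expectation of 30 RM/UM per arm, and a benefit confined to carriers in the genotype-supported arm. The value of k is unknown, so the range in the table is the finding, not any single row.

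It does not follow that the RM/UM between-arm calculation is wrong. That figure reproduces and is untouched by this point. What loses support is a summary of excellent power that goes beyond 80% at 0.74.

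**What to change.** In the power calculation of section 7, do one of two things:
- drop the 81% and >99% as efficacy power for this trial; or
- relabel them as a carrier v non-carrier comparison within the conventional arm (about 30 v 60) and restate them as 94% at 0.79 and 51% at 0.45. First settle on one acid-clearance effect size; if it is 0.49, the figure is 58%.

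In either case, rest the closing summary on the RM/UM between-arm calculation alone (80% power at an effect size of 0.74) and remove the description of the power as excellent.

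Dropping the figures is simpler and also removes the 0.45 v 0.49 discrepancy. Both options change wording only: sample size, conduct and the planned analysis stay as they are. The cost is that the stated power becomes less favourable.

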## 7. Research Plan:

The study is a randomized, open-label, comparative effectiveness clinical trial in 180 total patients with GERD or dyspepsia symptoms who will be randomized to either conventional or genotype-supported treatment of GERD and dyspepsia. A total of 120 patients will be enrolled in the UF Health Gastroenterology Clinics in Gainesville, and 60 will be enrolled in a parallel study (under separate IRB protocol) at Nemours Children's Hospital Gastroenterology Clinics in Orlando, FL. Each site will be responsible for overseeing patient care and research at their respective facility. All participants will have symptoms of GERD or related diseases and be candidates for PPI therapy or on PPI therapy with continued symptoms.

We will enroll a total of 180 patients between the UF Health and Nemours sites, which should allow for sufficient power to detect our efficacy endpoint (see power calculation below). We will also collect data from the health records for up to 24 months after enrollment on upper respiratory infection (cold), sore throat, strep throat, bronchitis, pneumonia, ear infection, acute sinusitis (sinus infection), bone fractures, renal function, and gastrointestinal infections for preliminary assessment of the effects of *CYP2C19*-supported PPI dosing on adverse effects. This exploratory arm will provide data to inform power calculations for a larger study focused on preventing PPI-associated adverse events through genotype-supported dosing.

**Inclusion Criteria.** A total of 120 patients with GERD or related symptoms will be enrolled at UF Health. An additional 60 patients will be enrolled at Nemours Children's Hospital Gastroenterology Clinics under a separate IRB protocol. For this protocol, any patient over the age of 17 who presents to GI clinic with GERD or related symptoms and is either 1) being initiated on PPI therapy or 2) continues to have symptoms despite PPI therapy will be considered eligible for the study.

Exclusion Criteria. This study will exclude patients who have had extensive esophageal or gastric surgery or any major chronic illness or condition that in the opinion of the gastroenterologist that would interfere with participation in the study.

Participant Recruitment Methods.

Prior to enrolling their patients, clinicians at participating GI clinics (investigators for this study) will be asked to complete surveys that assess their knowledge, attitudes, and beliefs as they relate to pharmacogenetics testing.

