Patients will be approached for participation at their GI clinic visit by the treating clinician and/or physician assistant. After providing informed consent, patients will be randomly assigned to either conventional treatment or genotype-supported PPI therapy using a randomization table. A 5-ml (one teaspoon) venous blood sample will then be drawn by a nurse, physician assistant, or phlebotomist. The patient will be asked to complete 3 surveys/questionnaires: the Reflux Disease Questionnaire (RDQ), Global Overall Symptom (GOS) scale, and a survey to assess knowledge, attitudes, and beliefs about pharmacogenetic testing. Patients will receive a total of \$25 for participating in this study. The \$25 VISA gift card will be provided after completing the final questionnaire. Patients in the control group may be withdrawn prior to completion if they or their physician elect to order the genetic test during the study. These patients would receive a \$10 VISA gift card for their participation up to the point of withdrawal.

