Assessment of PPI efficacy and adverse effects. Our primary outcome will be the effectiveness of PPI therapy, which will be determined via two questionnaires: RDQ and GOS scale, administered by study personnel at baseline and 12 weeks. The RDQ was developed to monitor treatment response over time and evaluates 6 symptoms (12 items) covering 3 domains: heartburn, regurgitation, and upper abdominal pain. Each symptom is evaluated using a 6-point Likert scale to assess frequency and severity over the previous week. Each symptom is rated from 1 (did not have) to 6 (severe), and the RDQ mean score is calculated as the mean response to the 12 items. The RDQ mean score thus ranges from 1 to 6 and has been psychometrically validated. The GOS scale evaluates 18 symptoms, with each rated from 1 (no problem) to 7 (very severe). Similar to the RDQ, the mean score is calculated as the mean response to the 18 items, with mean scores ranging from 1 to 7. Patient participation will end after they complete the approximate 12 week questionnaire. However, we will continue to

follow patients over 24 months through medical record review to assess adverse outcomes for occurrence of upper respiratory infection (cold), sore throat, strep throat, bronchitis, pneumonia, ear infection, acute sinusitis (sinus infection), bone fractures, renal function and gastrointestinal infections.

Metrics for assessing success of pharmacogenetic testing in clinical practice. We will test a variety of variables that will provide insight into attitudes and acceptability of pharmacogenetic testing. These will include: 1) percent of patients approached about the study who agree to participate; 2) surveys of patients and clinic staff on knowledge, attitudes, and beliefs about pharmacogenetic testing; and 3) the percent of the time a dosing recommendation for a patient in the genotype-supported arm is accepted by the clinician. Patients will be surveyed about knowledge, attitudes, and beliefs about pharmacogenetic testing using questionnaires on enrollment and at the end of their study participation. Clinic staff will be surveyed about knowledge, attitudes, and beliefs about testing at the beginning and end of the study.

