Genetic results and clinical decision support. Results will be entered in the participant's electronic health record; genotype results for participants in the control/conventional arm will not be made available to patients/families through the secure patient portal in the EMR to maintain blind status. PPI recommended dosing will be made available to GI providers in the EMR for genotype-guided dosing. PPI templates will include phenotype, genotype, dosing recommendations, and educational information. Participants in the conventional arm will be prescribed the conventional PPI dose.

To minimize risks associated with genetic studies, all results of genetic tests and patient data will be stored in a secure database which is accessible only to study investigators. Genotype and phenotype data will be stripped of all identifiers prior to submission to the NIH dbGAP repository.

Assessment of PPI adverse events and efficacy. Our primary outcome will be a directed interview and questionnaire by study personnel at baseline and every following week up to 12 weeks of participation for efficacy of PPI therapy and for adverse outcomes for the study period: upper respiratory infection (cold), sore throat, strep throat, bronchitis, pneumonia, ear infection, acute sinusitis (sinus infection), and gastroenteritis. We have experience using the questionnaire to evaluate the safety of PPI treatment in children. The prevalence of each respiratory and gastrointestinal symptom will be compared in participants receiving conventional vs. genotype-supported dosing. As secondary outcomes, the efficacy and safety (adverse event score) of PPI therapy will be determined from scores from patient and parent-proxy reported outcomes: the GASP-Q, the validated SN-5 Pediatric Sinonasal Symptom Survey and validated PedsQL™ Gastrointestinal Symptoms Module. Efficacy and adverse events questionnaires will be completed via an electronic questionnaire on a weekly basis and stored in REDCap.

At Nemours Children's Hospital continuous monitoring on study metrics will be offered by study staff. Study metrics will include Gasp-Q, PedsQL™ Gastrointestinal Symptoms Module, SN-5 Pediatric Sinonasal Symptom Survey and Safety Q.

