Statistical analysis. We will have two primary hypotheses tested in this pragmatic clinical trial: 1. Hypothesis: RMs (1 or 2 GOF alleles) in the genotype-supported arm have better GERD control than RMs in the usual care group 2. Hypothesis: PMs (1 or 2 LOF alleles) in the genotype-supported group have fewer adverse effects (composite of URI/GI infections, kidney adverse effects, bone fracture) than PMs in the usual care group. Continuous variables will be compared between the genotype-supported group and the usual care group using t-test, and categorical variables will be compared using the chi-squared test. The hypotheses will be tested by logistic regression analysis to estimate the odds ratios and 95% confidence intervals for GERD control rate in the RM patients between the two arms and for the adverse events between the PM patients between the two arms. Time to-event analysis will be performed using Kaplan Meier method and a Cox regression model. Significant covariates associated with the events will be adjusted for in the multivariable models. All analysis will be performed in SAS 9.4 (Cary, NC).

We will also have a composite analysis that is conducted in the same manner that combines efficacy and safety and tests the hypothesis that genotype supported PPI dosing leads to better PPI efficacy and safety, as determined by composite of refractory GERD, and adverse effects.

Finally, we will evaluate the influence of genotype-supported dosing recommendations and will evaluate the percentage of the time when a dosing recommendation was made and accepted by the treating clinician, to provide practical data on the willingness of clinicians to adopt this approach. We will also collect patient- and provider-level survey data on attitudes about pharmacogenetics testing; using survey tools adapted from those utilized by other IGNITE groups. These will be shared for network-wide analyses, but because of the number of patients we will study, we should also have sufficient data to perform analyses on our patients along.

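### The 80% power for the RDQ comparison counts 60 children for whom no RDQ is documented; on the 120 adults it is about 63%

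*Combined protocol and SAP*

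**What the plan says.** Under Analysis Plan and Power Calculations, the UF Health protocol tests its hypothesis by linear regression on RDQ reduction, comparing arms within RM/UM patients. The sample size argument is: "With 180 total patients (90 patients in each arm), we expect approximately 30 patients in each arm to have the genotype of interest". At alpha 0.05 this is said to give 80% power for an effect of at least 0.74, equated to 1.22 points for regurgitation and 0.93 for heartburn. Both are described as below the clinically significant level, and the study is judged well powered on that basis. The Research Plan likewise says of the 180 patients: "which should allow for sufficient power to detect our efficacy endpoint".

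On the instrument, the UF section on PPI efficacy states: "Our primary outcome will be the effectiveness of PPI therapy, which will be determined via two questionnaires: RDQ and GOS scale". The UF recruitment section has patients complete "the Reflux Disease Questionnaire (RDQ), Global Overall Symptom (GOS) scale" and a survey about pharmacogenetic testing. That protocol enrols patients over 17. The Research Plan places the other 60 patients in a parallel study at Nemours under a separate IRB protocol.

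The Nemours text (Study Design, Focus on Aim 2) covers children aged 5 to 17. Among its secondary outcomes, "the efficacy and safety (adverse event score) of PPI therapy will be determined from scores from patient and parent-proxy reported outcomes: the GASP-Q", together with the SN-5 and the PedsQL gastrointestinal module. A second list reads: "Study metrics will include Gasp-Q, PedsQL™ Gastrointestinal Symptoms Module, SN-5 Pediatric Sinonasal Symptom Survey and Safety Q". Its Statistical analysis paragraph has hypotheses "tested by logistic regression analysis to estimate the odds ratios and 95% confidence intervals for GERD control rate in the RM patients". Resource Sharing Plans permits exchange of de-identified data between the sites for cross-site analysis, but names no common efficacy score.

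**The concern.** Power for an RDQ comparison can come only from patients who have an RDQ score. One third of the 180 are children in a separately governed study whose listed instruments include neither the RDQ nor the GOS. If they contribute no RDQ, the RM/UM comparison has one third fewer patients than the power statement assumes.

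This is the only hypothesis test of efficacy in the UF protocol, and the claim of adequate power depends on the detectable differences of 1.22 and 0.93. If the real detectable differences are larger, a null result would be weaker evidence against genotype-supported treatment than readers would be led to believe.

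**Working it through.** **Inputs**

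- Effect 0.74, alpha 0.05, 180 patients, 90 per arm, about 30 RM/UM per arm: Analysis Plan and Power Calculations.
- Sites: 120 UF adults and 60 Nemours children: Research Plan.
- RM/UM share: Table 1 gives 28% + 5.3% = 33.3%; Genotyping and result reporting gives about 30% to 35%.
- Points per SD, from the plan's own equivalences: 1.22/0.74 = 1.65 for regurgitation; 0.93/0.74 = 1.26 for heartburn.
- Assumptions: two-sided test, 1:1 allocation among the adults, no dropout and no gain from covariate adjustment.

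**Method.** Two-sample t test with n per arm: noncentrality δ = d × √(n/2), with 2n − 2 degrees of freedom. Power is the probability that a noncentral t variable exceeds the two-sided 5% critical value in absolute size.

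**Reproducing the plan's figure.** With n = 30 and d = 0.74, δ = 0.74 × √15 = 2.87, the critical value is 2.00 and power is 80.5%. With n = 29 it is 79.1%. So 30 per arm is the smallest number that reaches 80%. A one-sided test with 30 per arm would give 88%, so the stated figure is two-sided. At a 33.3% share, 30 per arm requires 90 per arm, which is all 180 patients including every child.

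**Adults only.** 120 adults give 60 per arm, and 60 × 0.333 ≈ 20 RM/UM per arm. Then δ = 0.74 × √10 = 2.34, the critical value is 2.02 and power is 62.6%. The normal approximation gives 64.8%, and simulation of the t test gives 62.7%.

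| RM/UM per arm | Basis | Power at 0.74 | Effect detectable at 80% | Regurgitation | Heartburn |
|---|---|---|---|---|---|
| 30 | plan, 180 patients | 80.5% | 0.74 | 1.22 (stated) | 0.93 (stated) |
| 21 | adults, 35% share | 64.8% | 0.89 | 1.46 | 1.11 |
| 20 | adults, 33.3% share | 62.6% | 0.91 | 1.50 | 1.14 |
| 18 | adults, 30% share, or 10% lost from 20 | 57.8% | 0.96 | 1.58 | 1.21 |
| 16 | adults, 20% lost from 20 | 52.6% | 1.02 | 1.69 | 1.29 |

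The point differences are the detectable effect multiplied by 1.22/0.74 or 0.93/0.74. The losses of 10% and 20% are assumptions. The plan makes no dropout allowance, although it lets control patients be withdrawn if the genetic test is ordered for them during the study.

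**The other power figures in the section.** The 81% and >99% figures compare *17 carriers with non-carriers on pH measures. They are not arm-versus-arm comparisons on the RDQ, so they cannot fill the gap. They also contain a slip: acid clearance is given an effect size of 0.45, but 81% power is then quoted for 0.49. With 60 carriers and 120 non-carriers, the same method gives 80.8% at 0.45, 86.9% at 0.49 and 99.9% at 0.79.

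**The case against.** The plan's arithmetic is correct for 30 per arm; what is in dispute is who can supply the endpoint. That is so, but the stated power is still wrong for the patients with a documented RDQ.

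The absence of the RDQ at Nemours is inferred. No sentence says children will not complete it, and part of the Nemours design section was not in the text available to us. The Nemours primary outcome also includes an unnamed weekly interview and questionnaire covering efficacy, so its lists are not strictly closed. The Nemours Statistical analysis paragraph is written for the whole trial, and the power paragraph after it still assumes 600 participants, so it shows poor harmonization more than anything specific to children. These points limit the claim to what is documented. None of them supplies an RDQ or a common score for the children.

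It can also be said that 0.74 is a detectable effect and not an assumed true one, so power at 0.74 must fall when n falls. If the clinically relevant difference is larger, power there is better: with 20 per arm it is 79% at 0.9 and 87% at 1.0. This is fair, and it makes the rise in detectable effect to 0.91 the more useful result. The plan gives no threshold, so no reader can tell which power figure is the relevant one.

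Finally, the study is described as a pilot implementation, and combining 120 and 60 was openly intended. The intention is clear, but the endpoint and analysis that would make the combination usable are not written down.

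**Conclusion.** The concern holds. The plan counts 60 children toward RDQ power without a documented RDQ or common endpoint for them. On the 120 adults, power at 0.74 is about 63% rather than 80%, and 58% to 65% over the stated RM/UM share. The detectable effect is 0.91 (0.89 to 0.96), or about 1.50 points for regurgitation and 1.14 for heartburn. Eighty per cent power at 0.74 needs 60 RM/UM patients with an RDQ; 120 adults supply about 40.

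The claim of adequate power is unverified, not shown to be false, because the clinical threshold is not given. The figures rest on the assumptions listed with the inputs; any loss of week 12 scores lowers power further. The mismatch between 0.45 and 0.49 is real but secondary.

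**What to change.** Choose one of two routes and write it into the Research Plan and the power section.

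- **A. Only the adults complete the RDQ.** Restate power for 120 adults: about 20 RM/UM per arm, about 63% at 0.74 (58% to 65% over the 30% to 35% share), detectable effect about 0.91. State the clinically significant RDQ difference relied on and check 1.50 and 1.14 against it. Keep the favourable statements about power only if that check supports them. The cost is rewording and a less favourable number; no extra patients are needed.
- **B. The children are meant to contribute.** State that they complete the RDQ, or pre-specify a common efficacy endpoint with a site-stratified pooled analysis and its own power calculation. The cost is one added questionnaire for 60 children, or one pre-specified analysis with its power statement.

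Under either route, say that the 81% and >99% figures concern *17 carriers versus non-carriers on pH measures and do not support the arm comparison, and reconcile 0.45 with 0.49.
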